
LIST OF ABBREVIATIONS

AE	Adverse event
AIDS	Acquired Immunodeficiency Syndrome
ART	Antiretroviral therapy
CA-US RNA	Cell-associated unspliced HIV-1 RNA
CBC	Complete blood count
CD38	Cluster of differentiation 38
CD69	Cluster of differentiation 69
CFR	Code of Federal Regulations
CHEM-7	Basic metabolic panel (chemistry-7)
CRF	Case report form
DMC	Data Monitoring Committee
FDA	Food and Drug Administration
GCRC	General Clinical Research Center
GMP	Good Manufacturing Practice
HIPAA	Health Insurance Portability and Accountability Act of 1996
HIV	Human Immunodeficiency Virus
HLA-DR	Human Leukocyte Antigen-DR
HPLC	High performance liquid chromatography
ICF	Informed consent form
IEC	Independent Ethics Committee
IRB	Institutional Review Board
LFT	Liver function test
MS	Mass spectrometry
PBMC	Peripheral blood mononuclear cells
PI	Principal Investigator
PID	Participant identification
PD	Pharmacodynamics
PK	Pharmacokinetics
SAE	Serious adverse experience
SFGH	San Francisco General Hospital
SMC	Safety Monitoring Committee
SOP	Standard Operating Procedures
TCM	Traditional Chinese medicine
TSH	Thyroid stimulating hormone
UCSF	University of California, San Francisco

PROTOCOL SYNOPSIS

TITLE	Immunologic response to Euphorbia kansui powder prepared as tea in HIV-infected antiretroviral therapy (ART)-suppressed individuals: a dose escalation study
SPONSOR	Investigator Initiated Study ([name])
FUNDING ORGANIZATION	
 1. amfAR HIV Cure Institute 2. Salary support from K23 grant (K23GM112526) 3. Departmental Funds
NUMBER OF SITES	2 (1 coordinating site, UCSF, and 1 enrollment site, University of Utah)
RATIONALE	The key challenge of HIV eradication strategies is persistence of a small pool of resting memory CD4+ T cells that harbor latent replication-competent HIV. One potential strategy to eliminate this reservoir is “shock and kill” in which agents designed to reverse latency (latency reactivating agents, or LRAs) are combined with agents aimed at eliminating these virus-expressing cells. The goal of the current proposal is to evaluate the in vivo biological response to an herbal supplement used in traditional Chinese medicine (“kansui”) that has potent in vitro latency reactivating capabilities.
STUDY DESIGN	This is a phase I open label dose escalation study with a randomized, double-blinded, placebo-controlled crossover cohort.
PRIMARY OBJECTIVE	
 1. To determine the safety and tolerability of a single or 3 consecutive daily 1g doses of Euphorbia kansui extract powder, measured and prepared as tea, in HIV+ ART-suppressed individuals. 2. To determine the immunologic effect of a single or 3 consecutive daily 1g doses of Euphorbia kansui extract powder, measured and prepared as tea, in HIV+ ART-suppressed individuals.
SECONDARY OBJECTIVES	
 3. To determine the effect of a single or 3 consecutive daily 1g doses of Euphorbia kansui extract powder, measured and prepared as tea, on latent HIV in HIV-infected ART-suppressed individuals.
NUMBER OF PARTICIPANTS	N=8 total (The first N=2 participants will receive 1 dose for a total of 1 g; the final N=6 participants will receive 3 consecutive daily doses for a total of 3 g of Euphorbia kansui extract powder prepared as tea during the study period). Following enrollment of the first 2 participants, an interim analysis will be conducted to review all study data to determine if additional participants are needed to accomplish the study purpose, and if so, if enrollment should continue at the same

	
or a higher dose (i.e., next cohort).

PARTICIPANT SELECTION CRITERIA	
Inclusion Criteria:
 
1. Confirmed HIV-1 infection in adults aged 18 years or older.2. Continuous therapy with a DHHS recommended/alternative combination ART for least 36 months (at least 3 agents) at study entry with no regimen changes in the preceding 24 weeks.3. Maintenance of undetectable plasma HIV-1 RNA (<40 copies/ml) for at least 36 months. Episodes of single HIV plasma RNA 50-500 copies/ml will not exclude participation if subsequent HIV plasma RNA is <40 copies/ml.4. Two CD4+ T cell counts >350 cells/μl in the six months prior to screening. 
Exclusion Criteria:
 
1. Pre-ART viral load <2000 copies/ml (HIV controllers)2. Based on prior history and/or virologic testing, no alternative ART regimens are available in the event that the current ART regimen is compromised as a result of this study.3. Recent hospitalization in the last 90 days.4. Recent infection in the last 90 days requiring systemic antibiotics.5. Recent vaccination within the last 8 weeks prior to study screen or any study blood draw.6. Any known prior (lasting >6 months) or current history of liver-related diseases including but not limited to:
a. Hepatic cirrhosis of decompensated chronic liver diseasesb. Clinically active hepatitis B or C infection as evidenced by clinical jaundice or Grade 2 or higher liver function test abnormalitiesc. Any hepatic impairment, regardless of the graded liver function test abnormalities.7. Any known prior (lasting >6 months) or current history of gastrointestinal diseases including but not limited to:
a. History of diarrheal illness requiring the use of anti-motility agents including inflammatory bowel disease, chronic diarrhea not otherwise specified.b. History of gastrointestinal bleeding with hemoglobin below 12.5 g/dL.c. History of gastric or duodenal ulcersd. Inflammatory gastrointestinal disease such as Crohn's

	
disease or ulcerative colitis
 
8. Any significant renal disease (eGFR < 90 ml/min) or acute nephritis.9. Screening hemoglobin below 12.5 g/dL.10. Screening TSH consistent with hypothyroidism.11. Significant myocardial disease (current myocarditis or reduced left ventricular ejection fraction below the lower limit of normal) or diagnosed coronary artery disease.12. Significant respiratory disease requiring oxygen.13. Diabetes or current hypothyroidism.14. Participants of reproductive potential or breastfeeding. Women of childbearing potential must have a negative serum pregnancy test at screening. All participants of childbearing potential must agree to use a double-barrier method of contraception throughout the study period and up to 90 days after the last dose of kansui.15. Exposure to any immunomodulatory drug (including maraviroc) in the 16 weeks prior to study.16. Prior or current use of experiment agents used with the intent to perturb the HIV-1 viral reservoir.17. History of seizures, psychosis, abnormal electroencephalogram or brain damage with significant persisting neurological deficit18. Positive test for tuberculosis by either skin test (PPD) or blood interferon-gamma release assay (QuantiFERON).19. Significant substance use, which in the opinion of the investigator(s), is likely to interfere with the conduct of the study.
TEST PRODUCT, DOSE, AND ROUTE OF ADMINISTRATION	1 g of Euphorbia kansui extract powder, measured and reconstituted in 4 fluid ounces of boiled water allowed to cool and administered as tea, taken by mouth daily as either a single or 3 consecutive daily doses.
CONTROL PRODUCT, DOSE AND ROUTE OF ADMINISTRATION	Cohort 1: no placebo. Cohort 2: a placebo treatment arm will be assigned to patients in a randomized crossover design. The placebo will be decaffeinated black loose leaf tea which produces a tea that is similar in appearance, consistency, and (bitter) taste to kansui extract powder, without any known immune modulating properties or drug-drug interactions (e.g., changes in pH balance that might affect drug absorption) with HIV antiretroviral therapy.

DURATION OF PARTICIPANT PARTICIPATION AND DURATION OF STUDY	
Cohort 1: Participants will be on study for up to 45 days.
 
Screening: up to 14 days
 
Treatment: 1 day (participants to be admitted to the hospital during the day; no overnight stay)
 
Follow-up: 31 days after treatment dose day
 
Cohort 2: Participants will be randomized to either of two treatment arms, kansui or placebo, using a crossover design with a 56-day washout period in between treatment arms. Participants will be on study for up to 146 days.
 
Screening (for each arm): up to 14 days prior to treatment arm.
 
Treatment (for each arm): 3 days (participants to be admitted to the hospital each day; no overnight stays)
 
Follow-up (for each arm): 31 days after the initial dose for that treatment arm.
 
The total duration of the study is expected to be 1 year.

CONCOMMITANT MEDICATIONS	
Allowed:
 
 1. In the absence of drug-drug interaction information regarding kansui, participants may use their usual medications, as long as they are medically necessary and can be monitored safely during the study period. 
Prohibited:
 
 1. As stated in the exclusionary criteria above, participants may not have exposure to any immunomodulatory drug (including maraviroc) in the 16 weeks prior to study or during study period. 2. Also as stated in the exclusionary criteria, participants may not have prior or current use of experimental agents used with the intent to perturb the HIV-1 viral reservoir. 3. Participants may not be allowed to take anti-motility agents during the study period in order to accurately assess adverse events related to diarrhea. 4. Participants will not initiate new medications that may also cause diarrhea, including proton pump inhibitors, antibiotics, antidepressants, colchicine, digitalis, etc., during the study period. 
In addition to the above medications, per traditional Chinese medicine practices, participants should also not ingest ice-cold food or beverages, spicy foods, or seafood in the two days prior to, during, and up to two days after kansui treatment.

EFFICACY EVALUATIONS	
 • CD4+ and CD8+ T cell activation (expression of CD69, CD38, and HLA-DR). • Latent HIV reservoir quantification (cell-associated HIV RNA and plasma HIV RNA levels).
PRIMARY ENDPOINT	
 • Safety and tolerability of 1 g of Euphorbia kansui extract powder, prepared as tea, given as a single or 3 consecutive daily doses; no Grade 2 or greater clinical or laboratory adverse effects
SECONDARY ENDPOINTS	
 • Immunologic effect on CD4+ and CD8+ T cell activation (CD69, CD38, and HLA-DR expression on CD4+ and CD8+ T cells measured by flow cytometry). • Virologic effect on latent HIV Reservoir (cell-associated HIV RNA and plasma HIV RNA measured by rtPCR).
OTHER EVALUATIONS	With colleagues from the University of Utah Department of Pharmacology and Toxicology, the study team has begun developing an assay to measure levels of ingenol in participant plasma samples. Based on the bioassays performed in [name]'s lab at UCSF, the abundance of ingenol in Euphorbia kansui extract powder is estimated to be approximately 1:100. We will be storing plasma samples collected from this study in order to measure plasma ingenol levels post-dosing with kansui as part of later pharmacokinetic/pharmacodynamics analyses.
SAFETY EVALUATIONS	
Incidence of adverse events
 
Interim analysis following completion of Cohort 1

PLANNED INTERIM ANALYSES	During the study, safety will be monitored by a Safety Monitoring Committee (SMC), which will be led by an HIV specialist. The SMC will review all study procedures before the initiation of the study. They will have the full and final authority to stop the study for any safety concern at any point. Given the unknown safety profile of Euphorbia kansui , the first participant in each dosing level will complete 5 days of study prior to any further participants commencing the study. The decision to proceed with further drug administration will be taken by the Principal Investigators, taking into consideration clinical and laboratory adverse events. The decision to proceed with the next dosing level will be taken by the SMC. Specifically, dosing will be stopped and the SMC will be notified if one Grade 4 or two Grade 3 drug related adverse events or laboratory abnormalities are reported, if a participant develops virologic failure (defined as any HIV-1 RNA levels >200 copies/mL or a single HIV-1 RNA level >1000 copies/mL), becomes pregnant or initiates breastfeeding, or is required to initiate one of the prohibited concomitant medications listed in section 7.1. If stopping/pausing criteria are not met, the remainder of the dosing cohort will be enrolled/dosed the subsequent week. The study will proceed to the next dosing level provided the

	stopping/pausing criteria are not met. A University of Utah Department of Medicine faculty member who is not otherwise involved in the study and who will not communicate with the study investigators regarding any aspect of the SMC reports will prepare the monitoring reports. The SMC will review accrual, adverse events summaries, CD4+ T-cell counts and HIV RNA levels/suppression over time, off-study rates and completeness of follow-up, by dose cohort.
STATISTICS Primary Analysis Plan	[name] has expertise in epidemiology and biostatistics. She will be performing the data analysis for the study. Paired analyses using Wilcoxon signed rank tests will be performed to evaluate whether there is a statistically significant change in markers of immune activation (CD69, CD38, and/or HLA-DR) on CD4+ and CD8+ T cells after a 1 or 3 doses of Euphorbia kansui extract powder prepared as tea. Multivariate analyses will then be performed to evaluate the association between kansui and measures of immune activation at post-dosing, using linear mixed effects models, which account for within-participant correlation of observations and allows for greater stability in the estimate of the outcome measures within individuals. Similarly, for measures of the HIV reservoir, we will perform negative binomial mixed effects regression (a method to analyze over-dispersed count data) to compare the size of the latent HIV reservoir before and after kansui administration.
Rationale for Number of Participants	A total of 8 participants (2 from dosing cohort 1 and 6 from dosing cohort 2) will contribute to the analysis, with 8 or 25 timepoint measures, respectively. The within-individual variability will be reduced by use of the within-individual control measures, as well as the repeated measurements post-dosing. The primary outcome of the study will be an increase in the % T cell activation (CD38+ HLA-DR+) of CD8+ and CD4+ T cells. Based on our recent experience performing a phase 1 trial of canakinumab (an interleukin-1 beta inhibitor) to reduce inflammation in chronic HIV-infected ART-suppressed individuals, ¹ we estimate that we will have 80% power to detect a within-individual increase of 2.7 points in the % CD8+ T cell activation (standard deviation [SD] at 31 days of 1.6%). We will also assess virologic changes as secondary outcomes in the study. Based on data from our recent HIV latency phase 2b trial of disulfiram, ² we estimate that we will have 80% power to detect 0.6-0.7 log increases in cell-associated unsPLICED (CA-US) HIV RNA (SD=0.4 and 0.5 for Day 4 and Day 31, respectively), and a 0.6-0.5 log increases in ultra-sensitive plasma HIV RNA (SD=0.4 and 0.3 for Day 4 and Day 31, respectively).

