3 STUDY OBJECTIVES

3.1 Primary Objective

The primary objective is to assess the safety and tolerability of up to 3 consecutive daily doses of 1 g *Euphorbia kansui* extract powder prepared as tea in HIV-infected ART-suppressed participants.

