10 ADVERSE EXPERIENCE REPORTING AND DOCUMENTATION

10.1 Adverse Events

An adverse event (AE) is any untoward medical occurrence in a clinical investigation of a patient administered a pharmaceutical product and that does not necessarily have a causal relationship with the treatment. An AE is therefore any unfavorable and unintended sign (including an abnormal laboratory finding), symptom or disease temporally associated with the administration of an investigational product, whether or not related to that investigational product. An unexpected AE is one of a type not identified in nature, severity, or frequency in the current Investigator's Brochure or of greater severity or frequency than expected based on the information in the Investigator's Brochure.

The Investigator will probe, via discussion with the participant, for the occurrence of AEs during each participant visit and record the information in the site's source documents. Adverse events will be recorded in the patient CRF. Adverse events will be described by duration (start and stop dates and times), severity, outcome, treatment and relation to study drug, or if unrelated, the cause.

AE Severity

The National Cancer Institute's Common Terminology Criteria for Adverse Events (CTCAE) Version 3.0 should be used to assess and grade AE severity, including laboratory abnormalities judged to be clinically significant. The modified criteria can be found in the study manual. If the experience is not covered in the modified criteria, the guidelines shown in Table 1 below should be used to grade severity. It should be pointed out that the term "severe" is a measure of intensity and that a severe AE is not necessarily serious.

Table 1. AE Severity Grading

Severity (Toxicity Grade)	Description
Mild (1)	Transient or mild discomfort; no limitation in activity; no medical intervention or therapy required. The participant may be aware of the sign or symptom but tolerates it reasonably well.
Moderate (2)	Mild to moderate limitation in activity, no or minimal medical intervention/therapy required.
Severe (3)	Marked limitation in activity, medical intervention/therapy required, hospitalizations possible.
Life-threatening (4)	The participant is at risk of death due to the adverse experience as it occurred. This does not refer to an experience that hypothetically might have caused death if it were more severe.

AE Relationship to Study Drug

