A study data coordinator will produce administrative reports regularly describing study progress including the following: (1) accrual, (2) demographics, (3) study subject status, (4) laboratory data, and (5) number and type of serious AEs. Reviews will be communicated to the University of Utah and UCSF Committee on Human Research (CHR), study sponsor, and/or federal agencies, as appropriate. The SMC will have access to treatment assignment. The study will be discontinued if the SMC determines that it is in the best interest of the subjects.

Grade 1 or 2 AEs will not result in any change to the study plans. If there is evidence for a Grade 3 AE that is not caused by the study drug, the study will continue as planned. On

the other hand, Grade 3 AEs thought to be possibly caused by the intervention and any Grade 4 AEs will result in a hold on any future enrollments until a decision to proceed or to stop the study is made by the SMC

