14.3 Analysis of Primary Endpoint

The safety and tolerability data will be summarized by dosing cohort. Adverse events will be tabulated by dosing cohort and will include the number of participants for whom the event occurred, the rate of occurrence, and the severity and relationship to study drug. We may be underpowered to perform Fisher's exact tests to compare crude rates of adverse events between dosing cohorts or to perform adequate Cochran-Armitage trend tests for dose-toxicity.

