14.5 Sample Size

A total of 8 participants (2 in dosing cohort 1 and 6 in dosing cohort 2) will contribute to the analysis, with 8 or 25 timepoint measures, respectively. The within-individual variability will be reduced by repeated measurements post-dose. Based on existing data from our study population regarding the percent CD38+HLA-DR+ CD4+ T cells (standard deviation of 4.9%) in our study population and a paired, one sample, repeated measures analysis, we will have greater than 80% power to detect a 2.7% change in CD4+ T cell activation levels post-dose. Similarly, we will have greater than 80% power to detect a 17% change in cell-associated HIV-1 RNA and a 0.37% change in plasma HIV-1 RNA.

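### The primary safety criterion has no unit, window, attribution or phase, and Section 14.3 tabulates adverse events only by dosing cohort, which mixes kansui and placebo phases and gives no interval

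*Combined protocol and SAP*

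**What the plan says.** - **Endpoint.** The Primary Endpoint entry of the synopsis names the safety and tolerability of kansui, as one dose or three daily doses, and adds the criterion "no Grade 2 or greater clinical or laboratory adverse effects". Section 3.1 sets the matching objective ("The primary objective is to assess the safety and tolerability of up to 3 consecutive daily doses of 1 g") but names no grade.
- **Definition of an event.** Section 10.1 defines an adverse event "whether or not related to that investigational product". Grading covers clinical events and laboratory findings, "including laboratory abnormalities judged to be clinically significant". The synopsis says effects rather than events, and effects is not defined.
- **Analysis.** Section 14.3: "Adverse events will be tabulated by dosing cohort and will include the number of participants for whom the event occurred", together with the rate, severity and relationship to study drug. It does not mention the Grade 2 threshold, an interval, an acceptable rate or treatment phase. The only comparisons it names are between dosing cohorts, and it concedes that these may be underpowered.
- **Design.** Section 14.5: "A total of 8 participants (2 in dosing cohort 1 and 6 in dosing cohort 2) will contribute to the analysis". Under Section 4.1, Cohort 1 takes kansui only, while each Cohort 2 participant takes both kansui and placebo, in random order and double-blind.
- **Monitoring.** Section 13: "Grade 1 or 2 AEs will not result in any change to the study plans".
- **Replacement.** Section 11.3 replaces participants who withdraw before their last dosing day. Section 14.1, although titled for data sets, defines no safety set.

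**The concern.** The one operational statement of the primary endpoint cannot be scored as written. Two analysts could reach opposite answers from the same data, depending on whether they count unrelated events, placebo-phase events or events before dosing.

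The planned table does not settle this. A Cohort 2 row formed by dosing cohort is neither a kansui rate nor a placebo rate. The relationship column does not separate the phases either, because in Cohort 2 attribution is made by blinded staff. The crossover supplies a within-participant placebo control, but the primary endpoint analysis does not use it.

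At stake is what the trial can say about safety. A single Grade 2 event may be background noise, and a clean result may be compatible with common toxicity. The plan gives the reader no means of judging either.

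**Working it through.** The plan states no sample size, power, margin or acceptable rate for safety; its power figures concern T cell activation and HIV RNA. There is no figure of its own to reproduce.

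**Inputs.** From Sections 4.1 and 14.5: 8 kansui phases (2 single-dose, 6 three-dose) and 6 placebo phases, so 2 + 6 × 2 = 14 participant-phases. The background risk p of a Grade 2+ event per participant-phase is an assumption shown as a range, because the documents give none.

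**1. Chance that an inert tea shows at least one Grade 2+ event:** 1 − (1 − p)^n. The n = 14 column treats a participant's two phases as independent.

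| Assumed p | n = 8 kansui phases | n = 14, all phases |
|---|---|---|
| 1% | 7.7% | 13.1% |
| 2% | 14.9% | 24.6% |
| 5% | 33.7% | 51.2% |
| 10% | 57.0% | 77.1% |
| 20% | 83.2% | 95.6% |

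The chance reaches 50% when p = 1 − 0.5^(1/n), which is 8.3% for n = 8 and 4.8% for n = 14. Whether placebo-phase events count therefore changes the answer materially.

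**2. What zero events would exclude.** The exact (Clopper-Pearson) two-sided 95% upper limit is 1 − 0.025^(1/n):
- 0/8: 1 − 0.025^(1/8) = 36.9%
- 0/6 (three doses): 1 − 0.025^(1/6) = 45.9%
- 0/2 (one dose): 1 − 0.025^(1/2) = 84.2%

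This step needs no background rate. Put the other way, if the true risk is 10%, eight clean participants still occur with probability 0.9^8 = 43.0%; if it is 20%, with probability 0.8^8 = 16.8%.

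**3. Effect of tabulating by cohort.** A Cohort 2 participant has two phases in which an event can occur, a Cohort 1 participant one. With an inert tea and independent phases, the expected proportion with an event is p in Cohort 1 and 1 − (1 − p)^2 in Cohort 2: 5% against 9.75%, 10% against 19%, or 20% against 36%. The cohort comparison named in Section 14.3 would thus show an apparent dose difference that comes only from the extra phase.

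**The case against.** The strongest reply has four parts.

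**Section 14.3 is a real analysis.** It plans participant counts, a rate, severity and relationship, so Grade 2+ and related counts could be derived. This stands: it would be wrong to say that the endpoint goes unanalysed. What is missing is the criterion itself, the split by phase and an interval.

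**The synopsis line is about kansui.** Its subject is kansui after dosing, and it speaks of effects. A kansui-only, related-only reading is possible. A reader might infer that one unrelated or placebo-phase Grade 2 event fails the trial; the text does not say so. It does not exclude it either. Elsewhere the protocol limits by causality explicitly (Sections 10.4 and 13), and here it does not. The fault is ambiguity.

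**Nothing is triggered by the criterion.** Dosing holds and escalation rest on Grade 3 and 4 events, virologic failure and committee judgement, and Section 13 says that Grade 1 or 2 events change nothing. This stands and confines the consequence to interpretation.

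**Any trial of 8 has wide limits, and this one is presented as a pilot.** That is true, and Section 14.3 admits low power for comparisons. But wide limits are a reason to print them, and small size does not explain combining two treatments in one row.

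**Conclusion.** The point holds as one of definition and tabulation. The criterion lacks unit, window, attribution and phase. Section 14.3 does not evaluate it, and its by-cohort table combines kansui and placebo events in Cohort 2. With 8 participants an all-or-none reading is uninformative: a clean result leaves risks of up to 37% (0/8), 46% (0/6) or 84% (0/2) compatible with the data.

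Two stronger readings are tempting and not supported. One is that an inert tea would often fail. That depends on a background risk that the documents do not supply: the figure is 8% to 34% at assumed risks of 1% to 5%, and passes one half only above 8.3% for the kansui phases. Broad health exclusions, and the grading of only those laboratory findings judged clinically significant, may keep the risk low. The other is that a clean result would be declared proof of safety. Section 4.1 states a hypothesis that kansui will be safe and tolerable, but no rule draws that conclusion from zero events; the plan merely has nothing to guard against it.

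The upper limits rest only on the exact binomial and on 2, 6 and 8 evaluable participants. The background-risk figures also assume a common risk and independence between participants and, for all 14 phases, between phases.

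**What to change.** 1. Replace the all-or-none wording with a per-participant endpoint: at least one treatment-emergent Grade 2+ clinical or laboratory event from the first dose of a phase to the Day 31 or Day 132 visit that closes that phase. Show it for all events and for events at least possibly related. List events outside these windows separately.
2. In Section 14.3, tabulate by treatment phase: Cohort 1 kansui, Cohort 2 kansui, Cohort 2 placebo. Show the within-participant kansui/placebo pairs descriptively.
3. Report n/N with an exact Clopper-Pearson 95% interval for each row, and state in advance the upper limits for 0/2, 0/6 and 0/8.
4. Define the safety set as every dosed participant, including anyone later replaced under Section 11.3. A Cohort 2 participant replaced after one phase counts only in the phase received, so the kansui and placebo denominators may differ.

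The cost is some wording, one small table and a more modest safety claim. Dosing, visits and monitoring rules are unaffected.
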